**Can a novel telemedicine tool reduce disparities related to the
identification of preschool children with autism?**

NCT05373173

Protocol/Statistical Analysis Plan adapted from IRB application approved on
4/20/2022

Background

With the rising prevalence of Autism Spectrum Disorder (ASD), accurate identification and meaningful engagement of children and families in evidence-based services represents a pressing public health and clinical care challenge. Considerable emphasis has been placed on strategies to boost early ASD diagnosis in toddlers. However, early identification is hindered in part by vast phenotypic heterogeneity, wherein subtle ASD symptoms may not be readily identified via screening, surveillance, or parent concerns during the toddler years. Specifically, children without significant language delays, cognitive delays, or externalizing behaviors may not be flagged as for ASD concerns until the preschool years or later. In addition, pervasive service system limits such as a lack of trained providers and significant wait times for evaluation can delay definitive diagnosis for years. Despite advances in screening and awareness, the average age of diagnosis in many locations in the US remains later than four years of age. This is especially true for children from traditionally underserved communities (e.g., families in poverty, rural communities, racial/ethnic minorities, linguistically diverse families), who are much less likely to be diagnosed at young ages. These delays contribute to substantial family stress and restrict access to ASD intervention services critical for optimal short-term and lifespan functioning.

Ideally, universal ASD screening in toddlerhood would identify most children at-risk for ASD and then facilitate prompt diagnostic evaluation by a multi-disciplinary team of specialists. In reality, such diagnostic teams, or individual experts, are not readily available in most areas of the U.S. The standard of care in many community pediatric settings is to perform developmental surveillance, screen for risk, and then refer children to tertiary diagnostic centers with lengthy waitlists; meanwhile, without diagnostic confirmation, children may receive low levels of non-specific intervention or preschool services, or fail to engage with intervention and school services at all. Data suggest that the wait for ASD evaluation services dramatically increases as children age, with extended waits (i.e. over a year) common in the preschool period. Delays in diagnosis may contribute to more pronounced impairments and challenges accessing services (i.e. diagnostic delay associated more limited private/school-based intervention, higher rates of psychotropic medication use). Unfortunately, even when an appointment becomes available, multi-stressed, rural, or traditionally underserved families may not be able to make it to a tertiary care center. Powerful recent work suggests that addressing care disparities and systemic structural racism within models of ASD identification will require novel identification tools and processes that 1) include the preschool age span and 2) specifically target underserved groups at risk for tremendous diagnostic delays. For example, a recent study investigating a large cohort of African-American children in the U.S. found an average 3-year delay between first parental developmental concern and ASD diagnosis; half of parents reported seeing multiple providers before receiving an ASD diagnosis, and 31% reporting a lack of available professionals as a major contribution to this delay.

Study Purpose and Description

Innovative telemedicine practices could address many existing traditional barriers to ASD identification. Telemedicine has the potential to put linguistically and culturally

competent clinical expert virtual providers directly into communities during a critical window in which many vulnerable families may approach, or re-approach, care systems about developmental concerns that become more prominent with age. In the current proposal, we will develop and evaluate the potential clinical and familial value of a telemedicine-based ASD assessment tool, the **TAP-Preschool (TELE-ASD-PEDS-Preschool)**, designed to overcome traditional barriers to diagnosis and service access in underserved preschool populations that may not be readily identified or engaged by early screening and intervention systems.

A growing body of literature supports the use of telemedicine-based approaches to ASD assessment and intervention. This includes remote activities to assess infant social communication skills in the first year of life, coaching parents through administration of gold standard diagnostic tests, and provider coding and analysis of interactions that are video-recorded by caregivers. Results reflect high levels of caregiver and provider satisfaction and satisfactory agreement with traditional in-person evaluations, illustrating both the promise and feasibility of tele-assessment. However, most existing approaches are limited by a focus on screening rather than diagnosis, protocols requiring specific materials, or asynchronous analysis of submitted videos, which require resources that preclude broader use. Moreover, in current form, these tools are not designed or intended to yield a quantitative formal assessment of core ASD symptoms to support diagnostic decision-making. Further, although providers are increasingly exploring telemedicine approaches to ASD assessment in the context of the COVID-19 pandemic, there is limited published work to date on the use of real-time, caregiver-led ASD assessment in home settings *with diverse populations*. Our own work has focused almost exclusively on toddlers in this regard. Ultimately, very few viable tools with validated psychometric properties are available for use in current models of telehealth assessment and care.

Study Aims

In **Specific Aim 1**, we will generate optimally performing models and key behavioral targets for tool development. We will do this by applying machine learning models and the principles of feature engineering to a phenotypically rich clinical research data set of preschoolers with ASD and other developmental concerns (N=914: 594 ASD and 320 Non-ASD).

In **Specific Aim 2**, we will engage in a rigorous adaptation and translation approach to optimize design of the **TAP-Preschool**. We will include leading ASD assessment experts, providers dedicated to caring for underserved populations, and parents of preschool children with ASD from underserved racial/ethnic and linguistic groups. We will lead these groups in a design process in order to yield a set of interactive and play-based, parent-coached tele-assessment activities designed to 1) elicit observations tied to key computational features, 2) be deployed within a 30-minute timeframe, 3) employ inexpensive materials found in most homes, and 4) use accessible assessment instructions for real-time coaching of parents.

We will recruit 30 parent/child dyads (children ages 36 to 72 months) with existing diagnoses of ASD (n = 20) or other developmental concerns (n = 10) from our clinical

research database. Each participant will have recent data available from comprehensive evaluation tools (ADOS-2, cognitive functioning, adaptive skills). Children with and without ASD are included to provide information about TAP-Preschool usage across diverse phenotypic profiles. The sample size of 30 is deemed adequate for gathering detection of feasibility/acceptability issues and key feedback regarding measure modification for further validation.

Inclusion/Exclusion Criteria: Aim 2

Inclusion

- English/Spanish Speaking families
- Children 36-72 months of age
- access to a device capable of supporting Zoom
- already has participated in a diagnostic evaluation

Exclusion

- severe sensorimotor impairments

Specific Aim 3: Initial deployment, formative evaluation, and refinement of the TAP-Preschool:

We will deploy the preliminary *TAP-Preschool* with a small sample (n = 30) to assess acceptability/feasibility, potential clinical value for remote observation, and challenges that warrant revision. We will then use this data to modify the *TAP-Preschool* and deploy the refined tool with a new sample of clinically referred children (n=120). We will evaluate its ability to facilitate accurate telemedicine supported diagnostic decision-making.

We will recruit a novel sample (n = 120) parent/child dyads (children 36 - 72 months of age) referred for evaluation of ASD or developmental delays. These children and a primary caregiver will participate in a home-based tele-assessment session and a subsequent blinded in-person evaluation. We will again include English/Spanish speaking families with access to a device that will support Zoom.

Inclusion/Exclusion Criteria: Aim 3

Inclusion

- English/Spanish Speaking families
- Children 36-72 months of age
- access to a device capable of supporting Zoom
- has not participated in a diagnostic evaluation

-Exclusion

- severe sensorimotor impairments

Study Procedures

Initial deployment, evaluation, and refinement of the TAP-Preschool:

Consenting families will be scheduled for a single tele-assessment session with a consented licensed psychologist ("remote clinician") from our clinical research center

(n=10). This clinician will coach parents through the TAP-Preschool procedures. Although families will receive standard, basic support regarding tele-assessment procedures, they will not receive extensive training on the TAP-P prior to the session in order to mimic real-world use. All remote clinicians will be experts in ASD with training on the original TAP and ADOS-2 research reliability. Each clinician will participate in 3 sessions (2 children with ASD, 1 other developmental concerns). Clinicians will be blinded to child diagnostic status. Participating telemedicine clinicians in this aim will not be aware of the ratio (2:1 ASD vs. other DD) or recruitment status prior to evaluation ratings. As children will have existing diagnoses, no diagnostic feedback will be provided.

We will collect user data (caregiver, clinicians) on satisfaction, ease of implementation, and diagnostic certainty (clinicians only). Based on this feedback, we will modify the preliminary TAP-Preschool instructions and procedures as needed. To systematically measure acceptability and feasibility of use we will utilize an adapted Acceptability, Likely Effectiveness, Feasibility, and Appropriateness Questionnaire (ALFA-Q).⁵⁴ The ALFA-Q asks caregivers and clinicians to use a 5-point Likert scale to rate the instrument acceptability, effectiveness, feasibility, and appropriateness for ASD decision making. We will also solicit free-form input. Team leads will briefly interview each clinician and caregiver about their experiences. After each telemedicine evaluation, participating clinicians will view data from previous comprehensive evaluations. Clinicians will provide concrete task evaluation data regarding whether they were able to elicit such behaviors or information in the telemedicine evaluation process. It is important to note that diagnostic agreement rankings will include dichotomous (agree/disagree) and uncertainty data (Likert ratings). As in our previous preliminary feasibility/effectiveness trial, we will target >60% of providers agreeing with existing risk classification for ASD, <10% of ASD inaccurately identified with ASD, and >50% non ASD DD *with certainty* as key benchmarks for understanding potential meaningful clinical value. Based on this data, our investigative team will collaborate with our clinical design team to suggest instrument modifications.

The tele-assessment will take <45 minutes to complete.

The parent forms will take approximately 20 minutes to complete.

Assessment on psychometrics, clinical, and familial value of the TAP-Preschool (Novel Sample):

All consented families will complete an initial home-based tele-assessment visit via Zoom that includes the TAP-Preschool and a brief symptom-focused developmental interview with a consented clinician. The initial tele-assessment session includes interviewing and developmental assessment to mimic real-world use of TAP-Preschool. The visit is designed to take less than 90 minutes, with TAP-Preschool evaluation lasting <30 minutes. Although we will not limit length, we will time all sessions. After the session, the examiner will record the clinical diagnosis issued (ASD, other developmental concerns, or typical development) and complete two diagnostic certainty ratings, one dichotomous, the other continuous. All initial TAP-Preschool administrations will be recorded via Zoom, and 50% of administrations (randomly selected) will be co-scored by a blinded examiner, unaware of prior assessment results and diagnostic decision, to

evaluate inter-rater reliability. Within 7 days of the remote assessment, families will participate in an in-person diagnostic assessment including common comprehensive measures of ASD, cognitive skills, and adaptive behavior. We will randomly select 25% of families to participate in a remote home-based re-test with TAP-Preschool two weeks following initial administration.

Tele-assessment measures: Prior to the appointment, caregivers will complete a Demographics Questionnaire (i.e., age, gender, race/ethnicity, zip code, parent education) and a Medical History Form through a secure HIPAA-compliant web portal (REDCap). To reduce technology-related disruptions, research staff will talk to families before the visit about connectivity settings and recommended materials.

These will take approximately 20 minutes to complete.

In a single tele-assessment session modeled after our previous work, licensed clinicians will administer the TAP-Preschool, the Developmental Profile, 4th edition (DP-4), and a DSM-5 ASD interview. The DP-4 is a caregiver interview (birth – 21 years) that identifies developmental strengths and weaknesses in five core areas. The DSM-5 interview provides symptom-focused questions with developmental anchors pertinent to this age range. Immediately after the session, the clinician will complete a DSM-5 checklist indicating symptoms present and clinical diagnosis issued (ASD, other developmental concerns, or typical development). This form also contains dichotomous (certain/uncertain) and continuous (10-point Likert scale) certainty ratings. Clinicians will describe their satisfaction with the tele-assessment process (CSQ: Clinician Satisfaction Questionnaire).

The initial tele-assessment appointment with the psychologist will last approximately 90 minutes.

Blinded in-person assessment measures: The in-person examiner will be blinded to the tele-assessment diagnosis until after the in-person assessment. The diagnostic confirmation battery will include the Autism Diagnostic Observation Schedule, Second Edition (ADOS-2) (one module is chosen based on language ability), a cognitive measure (Mullen Scales of Early Learning or Differential Ability Scales 2nd Edition, the Vineland Adaptive Behavior Scales, Third Edition, and a DSM-5 ASD Interview. Immediately after the in-person session, the examiner will also complete a DSM-5 checklist and certainty ratings.

In-person appointments will last approximately 2-3 hours and will consist of traditional diagnostic evaluations for autism spectrum disorder.

Parent measures: Parents will complete the Parent Perceptions of Telehealth (PPT) and the Parent Service Satisfaction (PSS) surveys, used in our previous work, to assess perceptions of tele-assessment procedures after the telemedicine and in-person evaluations.

These parent forms will take approximately 10 minutes to complete.

Reporting of Adverse Events or Unanticipated Problems involving Risk to Participants or Others

All members of the research team will be trained and instructed to immediately report any adverse events to the PI. Adverse events will be reported to the IRB within seven days. The PIs, in communication with the study teams, will distinguish serious adverse events (SAE) from non-serious adverse events (AE). The PIs and Co-Is are licensed clinical psychologists with experience establishing adverse event and safety protocols in research projects. All project staff will have training in identifying potential adverse events and reporting procedures.

Should any study participant express concerns about the study or their participation or appear distressed during any study activities, the witnessing research team member will bring the matter to the attention of the PI, or designate at that time, to determine the appropriate course of action, which may include contacting local authorities in the case of imminent danger during a telemedicine appointment (suicidality, child neglect or abuse). Although not anticipated, serious adverse events would be documented and discussed with the IRB as soon as possible and reported to the IRB and NIH project officer within 48 hours.

Study Withdrawal/Discontinuation

Participants can withdraw from the study at any time. If a participant withdraws from the study, research team members will offer other options for having the child evaluated for ASD. If a clinician withdraws from the study they will not be asked to participate again in the current protocol.

Study participation may also be discontinued in the event of repeated technology failures during tele-assessment. Should technology fail (e.g., lost connection that cannot be re-established), we will contact families by phone to schedule a second attempt. If this is also unsuccessful, will document this as part of our ongoing data collection processes while also routing families to appropriate clinical referral pathways.

If a child is in distress (i.e., crying, falling to the floor, shouting) then research staff will take a break and/or consult parents for input/help on how to best soothe their child. The parent will always be given the option to take a break or end the evaluation if they think their child is too distressed to continue.

If a clinician thinks that the child appears to be too distressed to complete the evaluation, opportunities will be given to reschedule the assessment. If the parent declines, the clinician will note that the child was unable to complete the assessment and only data obtained will be included in the study while also routing families to appropriate clinical referral pathways.

Statistical Design and Power

In Specific Aim 2, we will collect user data (caregiver, clinicians) on satisfaction, ease of implementation, and diagnostic certainty (clinicians only). We will examine these data

descriptively (frequencies for satisfaction items; mean/SD for diagnostic certainty) and use them to inform modifications to TAP-P procedures.

In Specific Aim 3, we will benchmark acceptability/usability and preliminary clinical value and then perform rigorous evaluation of the TAP-Preschool relative to in-person evaluation. Our sample size has been determined to power primary analyses around estimates of accuracy, specific psychometric properties, as well as family experience. We will use receiver operating characteristic (ROC) curve analyses to determine a cut score for the optimal scoring method and evaluate characteristics utilizing the entire sample. We will examine agreements and corresponding sensitivity, specificity, and positive and negative predictive value. After estimated attrition of approximately 10%, 108 subjects (projected 65 ASD; 43 non-ASD) will be available for analysis. PPV and sensitivity will have a margin of error no larger than +/- 9.7%, and NPV and specificity will have a margin of error no larger than +/- 12.0%. Margin of error (half the width of a 95% confidence interval) calculations are based on preliminary data from prior data from tele-assessment of ASD and conservatively assuming 80% PPV and 80% NPV. For inter-rater and test-retest reliability, we will be able to measure percent agreement with a margin of error no larger than +/- 7.5% and Cohen's kappa within +/- 0.12. For estimating associations among factors potentially related to clinician diagnostic certainty and caregiver satisfaction, we will have 80% power to detect odds ratios larger than 1.37. All calculations use a two-sided significance level of 0.05 (See Statistical Design and Power for more detail).

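### The TAP-Preschool score behind the ROC cut score is not required to be fixed before the same clinician's caregiver interviews, so the tool's own AUC and cut score may be inflated

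*Combined protocol and SAP*

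**What the plan says.** Study Procedures, Tele-assessment measures (novel sample), places all three remote measures in one sitting with the family: "licensed clinicians will administer the TAP-Preschool, the Developmental Profile, 4th edition (DP-4), and a DSM-5 ASD interview". After the session the clinician completes a DSM-5 checklist, a diagnosis and certainty ratings. The novel-sample section gives the reason for combining the measures: "The initial tele-assessment session includes interviewing and developmental assessment to mimic real-world use of TAP-Preschool".

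The same section says that "50% of administrations (randomly selected) will be co-scored by a blinded examiner, unaware of prior assessment results and diagnostic decision". The stated purpose of this is to "evaluate inter-rater reliability".

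Blinded in-person assessment measures: "The in-person examiner will be blinded to the tele-assessment diagnosis until after the in-person assessment". The in-person battery consists of the ADOS-2, a cognitive measure, the Vineland-3 and a DSM-5 ASD interview.

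Statistical Design and Power: ROC analysis will "determine a cut score for the optimal scoring method and evaluate characteristics utilizing the entire sample".

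The documents do not name the primary TAP-Preschool scorer, the order of measures within the session, or the time at which the score is entered.

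**The concern.** A cut score belongs to the instrument. To estimate it, the TAP-Preschool score should reflect what was seen during TAP-Preschool. Here the person who probably scores the tool also hears the caregiver's DSM-5 symptom report and the DP-4 answers in the same session. If the score is entered or adjusted afterwards, some of the interview can pass into it.

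That matters more than usual because the reference diagnosis also draws on a DSM-5 interview, held within 7 days. Interview content that enters the index score is then shared with the reference standard. Blinding the in-person examiner to the tele-diagnosis does not close this path, because the shared information comes from the family and not from the first clinician.

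At stake is what the ROC result means. Part of the AUC would be that of the interview, and the chosen cut would suit a blend of tool and interview.

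**Working it through.** **1. Who supplies the ROC score.**
- Blinded co-scores exist for 50% of administrations, and their only stated use is reliability.
- The ROC uses the entire sample.
- Co-scoring presupposes a first scorer.

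The only score that can exist for every child under the described procedures is that of the administering clinician. This is a strong inference, not an explicit statement.

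**2. The plan's own precision figures.** Inputs from Statistical Design and Power: 108 analysable children (120 × 0.90), of whom 65 have ASD and 43 do not; assumed accuracy 80%; two-sided 5%. The half-width is 1.96 × √[p(1−p)/n].
- n = 65: 1.96 × √(0.16/65) = 9.72 points (plan: 9.7).
- n = 43: 1.96 × √(0.16/43) = 11.96 points (plan: 12.0).

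Both reproduce. They describe sampling error only; a bias in the score would not show in them, and more children would not remove it.

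**3. Possible inflation of the AUC.** All inputs in this step are assumptions; the documents give none of them. Let the recorded score be (1−w)T + wI, where T is the TAP-Preschool score unaffected by the interviews and I is the interview information. Both are normal with unit variance in each diagnosis group. T separates the groups by 1.2 SD, I separates them by 1.5 SD, and their correlation within group is ρ. Then

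d = [1.2(1−w) + 1.5w] / √[(1−w)² + w² + 2ρw(1−w)], and AUC = Φ(d/√2).

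| Leakage w | AUC, ρ = 0 | AUC, ρ = 0.5 |
|---|---|---|
| 0 | 0.80 | 0.80 |
| 10% | 0.83 | 0.82 |
| 20% | 0.86 | 0.83 |
| 30% | 0.88 | 0.85 |

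Worked example at w = 0.3, where the numerator is 0.84 + 0.45 = 1.29:
- ρ = 0: the denominator is √0.58 = 0.762, d = 1.694, AUC = 0.88.
- ρ = 0.5: the denominator is √0.79 = 0.889, d = 1.451, AUC = 0.85.

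**4. What the blinded co-scores can show.** Half of 108 is 54. In the projected ratio that is 32 to 33 children with ASD and 21 to 22 without. The formula in step 2 gives:
- sensitivity: 13.86 points (n = 32) or 13.65 (n = 33), about 14;
- specificity: 17.11 points (n = 21) or 16.71 (n = 22), about 17.

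For an AUC of 0.80 with 33 and 21 children, the Hanley-McNeil variance is [0.16 + 32(0.6667 − 0.64) + 20(0.7111 − 0.64)] / (33 × 21) = 2.436/693 = 0.00351. The half-width is 1.96 × 0.0593 = 0.12. The AUC inflation in step 3 is at most 0.08, so an unpaired reading of the blinded half could not settle the matter. A paired comparison in the same children uses the data better.

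**The case against.** **Leakage is not shown.** The documents list TAP-Preschool ahead of the interviews, and the post-session form is described without a TAP-Preschool score. Both fit scoring during administration. If clinicians already work that way, this path largely disappears. This stands, and it is why the point is worded as a possibility. The plan does not require that practice, though, and a reader of the results could not verify it.

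**Sensitivity and specificity may not be the tool's.** A reader might infer that every accuracy figure in the plan is contaminated. The documents do not support that. Only the ROC cut score is clearly tied to the TAP-Preschool score. The sentence after it, on agreement, sensitivity, specificity and predictive values, may refer to tele-diagnosis against in-person diagnosis. For that comparison the combined session is the proper index test.

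**Use alongside an interview is the intended use.** The plan says that the session mimics real practice, so a cut score from clinicians who also interview is a defensible target. This stands in part: it supports the combined session for the overall diagnosis and certainty ratings. It does not justify crediting interview information to the instrument. If the in-use score is the intended target, the plan should say so.

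**The inflation may be small.** The larger AUC figures need independence within diagnosis group. Two measures of ASD symptoms in the same child are plausibly correlated, and at ρ = 0.5 the inflation is smaller. This stands, and both columns are shown.

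**Reliability.** A reader might infer that agreement is inflated as well. Comparing an interview-influenced score with a blinded one would be expected to lower agreement, so that does not follow. The co-scores are a partial check already built in, but no accuracy analysis uses them.

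**Conclusion.** The concern holds in a limited form. The score that by inference feeds the ROC analysis has no protection from interview information, whereas the in-person examiner and the co-scorer are both blinded. The AUC and cut score credited to TAP-Preschool may therefore be too favourable.

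The size cannot be derived from the documents. With a true AUC of 0.80, an interview separation of 1.5 SD and leakage of 0 to 30%, the apparent AUC runs from 0.80 (no bias) to 0.88 under independence, or to 0.85 at a correlation of 0.5. These are illustrations, not estimates.

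The conclusion rests on two things that the plan leaves open: that the administering clinician is the primary scorer, and that scoring may follow or be revised after the interviews.

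**What to change.** 1. Name the primary TAP-Preschool scorer in the protocol.
2. Administer TAP-Preschool first, and time-stamp and lock its item scores before the DP-4 and DSM-5 interviews begin. REDCap, already used for caregiver forms, could hold the form. Leave the overall diagnosis and certainty ratings at the end, as now.
3. Pre-specify a sensitivity ROC on the blinded co-scores, as a paired comparison of the clinician's and the blinded scores in the same roughly 54 children. Report both. A difference could also reflect live against recorded viewing, so it should be read as a check and not as a measure of leakage.

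**Cost.** This is a cheap improvement. All 108 children stay in the primary ROC, and the planned margins of 9.7 and 12.0 points do not change. The downsides are a fixed session order with a short scoring pause, which departs slightly from free clinical practice, and a sensitivity analysis with margins of about 14 points for sensitivity and 17 for specificity. The order and lock have to be in place before data collection, because a score entered after the interviews cannot be separated from them later. Blinded scoring of all the recordings would then be the fallback, at greater cost.

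### The TAP-Preschool cut score is derived by ROC and evaluated in the same Aim 3 sample with no correction in the public text, so accuracy reported at that cut will tend to be modestly optimistic

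*Combined protocol and SAP*

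**What the plan says.** Under Statistical Design and Power, the plan will use ROC curves to "determine a cut score for the optimal scoring method and evaluate characteristics utilizing the entire sample". The next sentence adds: "We will examine agreements and corresponding sensitivity, specificity, and positive and negative predictive value". The expected analysis set is 108 children, 65 with ASD and 43 without. On precision, "PPV and sensitivity will have a margin of error no larger than +/- 9.7"%, with 12.0% for NPV and specificity, both "conservatively assuming 80% PPV and 80% NPV". The section describes the work as an intention to "perform rigorous evaluation of the TAP-Preschool relative to in-person evaluation" and states: "Our sample size has been determined to power primary analyses around estimates of accuracy".

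No part of the public text gives a rule for picking the cut, a cut fixed beforehand, a hold-out set, cross-validation, a bootstrap correction or a later validation sample. The score range and the candidate scoring methods are also not given. Specific Aim 1 uses 914 existing records for models and behavioural targets, but is not said to supply a cut or a final scoring method. The section closes with a pointer, "See Statistical Design and Power for more detail", to fuller text that is not in the public document.

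**The concern.** A cut picked because it performs well in a sample partly fits the chance features of that sample. Evaluating it on the same children carries that good fortune into the reported accuracy. The resulting error is systematic and favours the tool, whereas a margin of error describes random error only. Clinicians who adopt a published cut would rely on its sensitivity, specificity, PPV and NPV, and at least some of these would on average be too high.

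Two gaps make the size hard to judge from the plan. It does not say which data select the scoring method. Nor does it say whether the four accuracy measures describe the ROC cut or the remote clinician's diagnosis, which needs no cut.

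**Working it through.** **1. The plan's own precision figures.** The inputs are 120 enrolled, 10% attrition, a 65/43 split and a proportion of 0.80, all from Statistical Design and Power and Specific Aim 3.

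- 120 × 0.90 = 108.
- 1.96 × √(0.8 × 0.2 / 65) = 9.72%, stated as 9.7%.
- 1.96 × √(0.8 × 0.2 / 43) = 11.96%, stated as 12.0%.

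Both reproduce. They are half-widths for a fixed proportion. That suits a pre-set cut or the tele-diagnosis. If they are meant for the ROC cut, they make no allowance for choosing it in sample.

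**2. Assumptions for the size of the bias.** The documents give no cut rule, score range or true accuracy at the cut. The following are therefore assumed: equal-variance binormal scores, one scoring method, sensitivity and specificity both 80% (d' = 1.683) or both 90% (d' = 2.563) at the best cut, and 10, 16, 30 or 200 score levels. Optimism is the apparent value minus the true value at the chosen cut. The simulation used 65 and 43 children, with 12,000 replicates at each of 12 score placements (10,000 replicates at 200 levels).

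Link to the plan's 80% PPV and NPV: if P children test positive, 0.8P + 0.2(108 − P) = 65, so P = 43.4 / 0.6 = 72.3. Then sensitivity = 0.8 × 72.3 / 65 = 89.0% and specificity = 0.8 × 35.7 / 43 = 66.4%, giving d' = 1.650, close to the 80% case.

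**3. Optimism in points, over all settings.**

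| Cut rule | Sensitivity | Specificity | PPV | NPV |
|---|---|---|---|---|
| Youden | 0.1 to 2.5 | 0.1 to 3.9 | 0.2 to 2.7 | 0.3 to 3.5 |
| Closest to corner | 0.0 to 2.0 | 0.0 to 3.0 | 0.1 to 2.0 | 0.2 to 2.6 |
| Highest cut keeping sensitivity ≥90% | 0.2 to 1.4 | −0.2 to +0.2 | 0.0 to 0.4 | 0.3 to 1.5 |
| Cut fixed in advance | 0 | 0 | 0.1 | 0.2 to 0.3 |

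**4. Dependence on score levels** (Youden, sensitivity / specificity).

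| Levels | 80% accuracy | 90% accuracy |
|---|---|---|
| 10 | 0.4–1.4 / 0.6–2.0 | 0.1–1.2 / 0.1–1.7 |
| 16 | 1.3–1.8 / 1.9–2.5 | 0.8–1.2 / 1.2–1.8 |
| 30 | 1.7–2.0 / 2.7–3.1 | 1.3–1.5 / 1.9–2.3 |
| 200 | 2.5 / 3.8–3.9 | 1.9 / 2.9 |

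At d' = 1.650 the Youden values are 1.0/1.3, 1.5/2.3 and 2.7/3.9 at 10, 16 and 200 levels. A separate simulation with a continuous score at 80% gave 2.7/4.3.

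**5. What moves it outside this range.** With 70% true accuracy, the largest values were 4.8 points for specificity and 5.8 for NPV. If the best of 3 to 5 equally accurate scoring methods (assumed correlation 0.5 to 0.8) is also picked in sample at 80% accuracy, Youden gives 2.6 to 5.1 for sensitivity and 4.1 to 7.8 for specificity.

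The near-zero specificity result for the sensitivity-target rule is special to the form in step 3, where the cut depends on the ASD children only. Choosing the best Youden value subject to sensitivity ≥90% gave +1.4 to +1.8 for specificity on a fine score.

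**6. Does resampling remove it?** Repeating the cut selection in each bootstrap resample changed the Youden bias at 80% (sensitivity/specificity) as follows:

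- 10 levels: 0.9/1.5 to −0.1/0.0.
- 16 levels: 1.5/2.3 to 0.3/0.4.
- 200 levels: 2.5/3.9 to 0.7/1.2.

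Over 18 scenarios (three rules, two accuracies, and 10, 16 or 200 levels), coverage of 95% intervals was:

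| Interval | Sensitivity | Specificity |
|---|---|---|
| Wilson, uncorrected | 94.2–97.2% | 93.6–96.9% |
| Wilson at the corrected value | 90.6–95.8% | 93.4–95.8% |
| Basic bootstrap | 86.6–94.2% | 82.6–92.8% |

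Root-mean-square error (Youden, 80%), apparent to corrected, went from 4.96 to 5.04 for sensitivity and 5.95 to 6.07 for specificity at 10 levels. At 200 levels it went from 5.46 to 5.03 and from 6.49 to 5.83.

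**The case against.** The strongest reply is that the key accuracy figures may not concern the cut at all. Specific Aim 3 sets out to "evaluate its ability to facilitate accurate telemedicine supported diagnostic decision-making", both clinicians issue diagnoses, and the margins rest on earlier tele-assessment data. If the four measures describe the tele-diagnosis, they and both margins carry no cut-selection bias. This stands as a limit on scope. It does not dispose of the point, because the ROC sentence itself evaluates the cut in the full sample and the accuracy list follows directly without naming an index test.

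Second, the effect is small, and values near 4 points need a near-continuous score. This stands. Third, correction brings no gain in total error when the score is coarse, and the corrected interval can cover slightly less well. This also stands, so the case for correction rests on removing a one-directional bias. Fourth, deriving a first cut on every available child is ordinary in formative work. That is a reason to keep the full sample, but not to present apparent accuracy as a rigorous evaluation.

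A reader might also infer that the plan has no correction anywhere. The documents do not support that, since the fuller statistical text they point to was not supplied.

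**Conclusion.** The concern holds as a modest upward bias in point estimates at the ROC cut, and it should be fixed. Its size is roughly 0 to 4 points under binormal scores, 80% to 90% accuracy and a single scoring method. Score granularity matters as much as the cut rule: at 10 to 16 levels it is about 0 to 2.5 points. The range is not a bound, because lower true accuracy or in-sample choice of scoring method takes it higher. In every scenario run it stayed below the corresponding 9.7 or 12.0 point margin.

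Three stronger readings are tempting but unsupported. One is that the confidence intervals fail: uncorrected Wilson intervals kept about 94% to 97% coverage. Another is that all of the study's accuracy results are inflated: the tele-diagnosis is untouched. The third is that a sensitivity target protects specificity in general: it does so only as the highest cut that keeps the target.

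Confidence is medium, because the cut rule, score range and index test are unstated.

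**What to change.** Keep the entire sample and add to the SAP:

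- the rule for choosing the cut, named in advance, and the data that select the scoring method;
- repetition of the cut selection, and of the scoring-method choice if made on these data, inside each bootstrap resample or cross-validation fold;
- optimism-corrected sensitivity, specificity, PPV and NPV, shown beside uncorrected values labelled as apparent (derivation-sample) estimates;
- an interval method fixed in advance, avoiding the basic bootstrap interval;
- which index test, cut score or tele-diagnosis, each accuracy figure and the 9.7% and 12.0% margins describe.

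If the fuller statistical text already contains a correction, it should be moved into the public plan.

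The cost is a few lines of text and a little programming, with no extra participants. Reported accuracy at the cut will be slightly lower. Some optimism remains with a fine score (up to 0.7 points for sensitivity and 1.2 for specificity), so confirmation in a new sample is still needed. With a coarse score the correction adds slight variance and does not reduce total error.
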